10.11. Appendix 11: Protocol Amendment History

DOCUMENT HISTORY	
Document	Date
Amendment (b)	28-September-2021
Amendment (a)	08-September-2021
Original Protocol	18-May-2021

Amendment (a)

This amendment is considered to be substantial.

The amendment is considered to be substantial because it is likely to have a significant impact on the

- scientific value of the trial,
- conduct or management of the trial

Overall Rationale for the Amendment:

Section # and Name	Description of Change	Brief Rationale
1.1. Synopsis; 4.1. Overall design; 9.5. Sample Size Determination	Amended statement “approximately 40 evaluable participants complete both Part A and Part B of the study”. Removed word “both” throughout.	Corrected error.
1.1. Synopsis; 1.3. Schedule of Activities; 4.1. Overall design	Adipose thickness will be measured by ultrasound. Option to measure by caliper deleted.	Clarification.
1.3. Schedule of Activities (Part A)	Time windows for VAS score collection updated.	Clarification.

CCI

1.3. Schedule of Activities (Part A)	On Day -1, deleted the dosing day exclusion/withdrawal criteria check as continued eligibility will be checked	Corrected error.
2.2. Background	Deleted “depending on the type of reaction” from section detailing the reported ISRs in the PRONTO-Pump-2 study.	Clarification.
5.2. Exclusion Criteria	Criterion 13: amended from severe neuropathy to have a pathologic tuning fork test. Criterion 18: serum creatinine value in $\mu\text{mol}/\text{L}$ unit updated to 1 decimal place. Criterion 29: added new criterion to exclude use of Lyumjev.	Criteria 13 and 29: ethics committee request. Criterion 18: clarification.
8.2.5.3. Local Infusion Site Reactions	Amended to state local infusion site reactions will be recorded as AEs as	BfArM request.

Section # and Name	Description of Change	Brief Rationale
8.3.1. Timing and Mechanism for Collecting Events	clinical indicated and not only if they qualify as SAEs.	BfArM request.
10.2. (Appendix 2) Clinical Laboratory Tests	Timing for reporting SAEs to Sponsor amended to “Immediately, without undue delay, and under no circumstances later than 24 hours of awareness”.	Clarification.
10.3. (Appendix 3) Adverse Events	Ethanol testing and urine drug screen deleted from table of laboratory tests as this table refers to local and central testing only. These tests will be performed at site using a breathalyzer or dip stick.	BfArM request.

2. ABBREVIATIONS

Abbreviations pertain to the Statistical Analysis Plan (SAP) only (not the tables, figures and listings [TFLs]).

AE	Adverse event
CI	Confidence interval
CRU	Clinical Research Unit
CSII	Continuous subcutaneous insulin infusion
CSR	Clinical Study Report
CV	Coefficient of variation
ECG	Electrocardiogram
ICH	International Conference on Harmonisation
ISR	Infusion site reaction
LSMeans	Least-squares means
MedDRA	Medical Dictionary for Regulatory Activities
SAP	Statistical Analysis Plan
SD	Standard deviation
T1D	Type 1 diabetes mellitus
TFLs	Tables, Figures, and Listings
VAS	Visual analog scale
WHO	World Health Organization

3. INTRODUCTION

This SAP has been developed after review of the Clinical Study Protocol (final version dated 18 May 2021, protocol amendment (a) dated 08 September 2021, protocol amendment (b) dated 28 September 2021 and protocol amendment (c) dated 14 October 2021).

This SAP describes the planned analysis of the safety and tolerability data from this study. A detailed description of the planned TFLs to be presented in the clinical study report (CSR) is provided in the accompanying TFL shell document.

The intent of this document is to provide guidance for the statistical analyses of data. In general, the analyses are based on information from the protocol, unless they have been modified by agreement with Eli Lilly and Company. A limited amount of information concerning this study (e.g., objectives, study design) is given to help the reader's interpretation. For open-label studies, this SAP must be signed off prior to first participant visit for this study. When the SAP and TFL shells are agreed upon and finalized, they will serve as the template for this study's CSR.

This SAP supersedes the statistical considerations identified in the protocol; where considerations are substantially different, they will be so identified. If additional analyses are required to supplement the planned analyses described in this SAP, they may be performed and will be identified in the CSR. Any substantial deviations from this SAP will be agreed upon with Eli Lilly and Company and identified in the CSR. Any minor deviations from the TFLs may not be documented in the CSR.

This SAP is written with consideration of the recommendations outlined in the International Conference on Harmonisation (ICH) E9 Guideline entitled Guidance for Industry: Statistical Principles for Clinical Trials¹ and the ICH E3 Guideline entitled Guidance for Industry: Structure and Content of Clinical Study Reports².

4. STUDY OBJECTIVES AND ENDPOINTS

4.1 Part A

4.1.1 Primary Objective and Endpoint

Primary Objective

To investigate local infusion site pain for infusions of sodium citrate and treprostinil in Humalog diluent with magnesium chloride (without insulin) in the abdominal, arm, thigh, and buttock areas in participants with type 1 diabetes mellitus (T1D) on continuous subcutaneous insulin infusion (CSII).

Primary Endpoint

VAS pain score.

4.1.2 Secondary Objective and Endpoint

Secondary Objective

To investigate local infusion site pain of 2 different cannula insertion depths (6 mm and 9 mm) in participants with T1D on CSII.

Secondary Endpoint

VAS pain score.

4.1.3 Exploratory Objective and Endpoint

Exploratory Objective

To assess local infusion site reactions (ISR) using the exploratory **CCI** Platform.

Exploratory Endpoint

Characterization and measurement of incidence and severity of local ISR data.

5. STUDY DESIGN

Study I8B-MC-ITTC is a 1-/2-center, participant-(Part A CCI) and investigator- CCI blind, 2-part randomized crossover study in adults (18 to 69 years of age, inclusive) with T1D on CSII. Approximately 46 participants will be randomly assigned to study intervention such that approximately 40 evaluable participants complete Part A CCI

[REDACTED]

Part A of this study will be a 1-/2-center, randomized, 1 day 5-period crossover based on the order of infusion sites and depths, blinded (between infusion depths), open-label single-treatment study conducted in adults with T1D.

CCI

[REDACTED]

For CCI Part A CCI, the participant will continue using his or her personal insulin pump system at the currently employed infusion site and will be responsible for performing the required actions to maintain its functionality. Participants will be instructed to avoid the use of the central abdominal area for their personal infusion sets during the CCI [REDACTED] and prior to arrival at the clinical research unit (CRU).

5.1 PART A

1. Following an informed consent and a screening visit, participants will come to the CRU in the evening (after dinner) of Day -1 for Part A.
2. Prior to the insertion of the first infusion set, the thickness of the SC adipose tissue layer at the abdomen, arm, thigh, and buttock areas will be assessed by ultrasound and the measurement recorded in mm in the electronic case report form. The evaluated site should be identified with a unique identifier.
3. The infusion sites will be assessed, and an image of each local infusion site will be collected using the CCI [REDACTED] Platform prior to insertion of the corresponding infusion set.
4. Each Medtronic™ MiniMed™ 770G pump reservoir will be filled by a qualified site staff member with 3 mL of study treatment (sodium citrate and treprostinil in Humalog diluent with magnesium chloride [without insulin]).
5. Five pumps will be used for each participant to assess infusions into the abdominal, arm, thigh, and buttocks areas. Participants will be randomly assigned to 1 of 5 infusion site sequences to indicate the order of the infusion sites being evaluated.
6. Six mm cannula will be inserted into each of the designated areas (abdomen [at least 5 cm away from the umbilicus in the left or right lower quadrants], posterior aspect of the upper arm, anterior or lateral thigh, and upper buttock), avoiding areas of lipohypertrophy or surgical scars. At the abdominal area only, a 9 mm cannula will also be inserted into the opposite side of the lower abdomen.

7. The first infusion site will be initiated, and a basal infusion rate of 1 U/h will be started. The same procedure will occur at the subsequent infusion sites according to the randomly assigned sequence with an approximately 30-minute interval between initiation of the previous infusion site. In case of immediate infusion set intolerance, a new infusion set can be inserted within the first 10 minutes of initiation of the infusion site.
8. Approximately 3 hours after the start of the basal infusion at 1 U/hr, a bolus dose of 15 U will be delivered at quick bolus speed (15 U/min) to each infusion site according to the treatment sequence with an approximately 30-minute interval between infusion sites.
9. A second bolus of 15 U given at quick speed (15 U/min) will be delivered approximately 6 hours after the start of the basal infusion to each infusion site according to the treatment sequence with an approximately 30-minute interval between infusion sites.
10. A third bolus dose of 15 U given at quick speed (15 U/min) will be delivered approximately 9 hours after the start of the basal infusion to each infusion site according to the treatment sequence with an approximately 30-minute interval between infusion sites.
11. Participants will rate the pain at each infusion site after each bolus dose at the following approximate time points: 5 minutes before the administration of a bolus dose and 1 and 15 minutes after the start of each bolus dose.
12. Study infusion sets with cannula and pumps will be removed.
13. Infusion sites will be evaluated for acute local ISRs and an image of each local infusion site will be collected using the CCI Platform.
14. Following the final evaluation, the participants will have the option to spend the night or be discharged from the CRU.

6. INFUSION SITE LOCATIONS/TREATMENTS

The following is a list of the study infusion site locations/treatment abbreviations that will be used in the TFLs.

6.1 Part A

Infusion site location	Infusion site location order in TFL
Arm	1
Thigh	2
Abdomen 6 mm	3
Abdomen 9 mm	4
Buttock	5

CCI

7. SAMPLE SIZE JUSTIFICATION

Approximately 46 participants with T1D will be enrolled in Study I8B-MC-ITTC so that approximately 40 participants complete CCI Part A CCI of the study. CCI

Forty completing participants will provide approximately 80% power to demonstrate approximately a 55% increase in the VAS pain score between the infusion site locations in Part A CCI. Testing will be done at alpha-level of 0.05 with a 2-sided confidence interval (CI). The variability was estimated by analyzing a Lilly internal study that showed a log-scale standard deviation of within- participant difference in VAS pain scores of 0.95.

Participants who discontinue the study before completing the assessments may be replaced at the discretion of the sponsor and investigator to ensure that approximately 40 participants complete the study. The replacement participant will be assigned to the same treatment sequence as the discontinued participant

8. DEFINITION OF ANALYSIS SETS

The “Full” analysis set will consist of all randomized participants. Participants will be included in the analyses according to the randomly assigned sequences.

The “Safety” analysis set will consist of all randomized participants who receive at least 1 infusion. Participants will be analyzed according to the infusions they actually received.

Data related to a site where an infusion set cannula is accidentally pulled out of an infusion site or data following a pump occlusion alarm during a bolus infusion will not be used in the analysis for that particular site only/part of the study.

All protocol deviations that occur during the study will be considered for their severity/impact and will be taken into consideration when participants are assigned to analysis populations before database lock.

9. STATISTICAL METHODOLOGY

9.1 General

Data listings will be provided for all data that is databased. Summary statistics and statistical analysis will only be presented for data where detailed in this SAP. For continuous data, summary statistics will include the arithmetic mean, arithmetic standard deviation (SD), median, min, max and n; for log-normal data, the geometric mean and geometric coefficient of variation (CV%) will also be presented. For categorical data, frequency count and percentages will be presented. Data listings will be provided for all participants up to the point of withdrawal, with any participants excluded from the relevant population highlighted. Summary statistics and statistical analyses will generally only be performed for participants included in the relevant analysis population. For the calculation of summary statistics and statistical analysis, unrounded data will be used.

Mean change from baseline is the mean of all individual participants' change from baseline values. Each individual change from baseline will be calculated by subtracting the individual participant's baseline value from the value at the timepoint. The individual participant's change from baseline values will be used to calculate the mean change from baseline using a SAS procedure such as Proc Univariate.

Data analysis will be performed using SAS® Version 9.4 or greater.

9.2 Demographics and Participant Disposition

Participant disposition will be summarized and listed. The demographic variables age, sex, race, site ID, body weight, height, and body mass index will be summarized by part and listed. All other demographic variables will be listed only.

9.3 Safety and Tolerability Assessments

9.3.1 Primary Endpoint

Descriptive statistics

Infusion site pain assessed using the VAS pain score will be listed and summarized using standard descriptive statistics including the geometric mean and CV% by bolus time (3, 6, and 9 hours after initiation of basal infusion) and VAS assessment time point (5 minutes prior to bolus and 1 and 15 minutes after bolus). For Part A, the summary will also be by infusion site location. The 5 infusion site locations include the assessment of 2 cannula depths at the

abdominal site. CCI

[REDACTED]
The relevant timepoint windows will also be displayed in the labelling of the timepoints in the output.

It is possible that VAS scores will be 0; if so, all scores will be analyzed as log (VAS+1) to allow for the inclusion of the 0 values in the geometric descriptive statistics. This transformation will be applied for the calculation of the geometric statistics only and will not be applied to the arithmetic statistics. This transformation (VAS+1) will also be applied to all data prior to the calculation of the ratio of the post-bolus time points to the pre-bolus time point if there are occurrence of 0.

Frequencies and percentages of VAS pain scores in each of the categories of 0, 1 to 10, 11 to 20, 21 to 45, and 46 to 100 mm will be summarized by bolus time, infusion site location/study treatment, and time point.

Geometric mean profile plots will be presented by bolus time, infusion site location/study treatment, and time point.

Statistical Analysis

A mixed effects model will be used to analyze the log transformed VAS pain score for each bolus time and VAS time point. The statistical model for Part A will include terms for infusion site location, period (order of infusions), bolus time, VAS time point, the 2- and 3-way interactions between infusion site location, bolus time, and VAS time point as fixed effects and participant as a random effect. Comparisons will be made between infusion site locations for the abdominal infusion site for each bolus time and VAS time point.

CCI

[REDACTED]
Least-squares means (LSMeans), infusion site location/treatment differences in LSMeans, and the corresponding 95% confidence intervals (CIs) for the infusion site location/treatment differences will be estimated and back-transformed from the log scale to provide estimates of the ratio of geometric LSMeans and 95% CI for the ratio of these means. It is possible that VAS scores will be 0; if so, all scores will be analyzed as log (VAS+1) to allow for the inclusion of the 0 values in the analysis.

The same model will also be used to analyze the change from the pre-bolus time point (5 minutes prior to the bolus) to the post-bolus time points of (1 and 15 minutes after bolus).

Example SAS code for Part A is shown below, CCI

```
proc mixed data=xxxx;
class location period bolus_time vas_time subjid;
model logVAS = period location|bolus_time|vas_time /residual ddfm=kr2;
random intercept / subject=subjid;
lsmeans location*bolus_time*VAS_time / cl pdiff alpha=0.05;
ods output lsmeans=lsm;
ods output diff=estims;
run;
```

9.3.2 Secondary Endpoint

For Part A, the comparison of cannula depths at the abdominal infusion site location will be analyzed as part of the same mixed effects model used for the primary endpoint.

9.3.3 Exploratory Endpoint

Local ISR data (erythema, induration, categorical pain, pruritus, and edema) will be listed and summarized by infusion site location (Part A) CCI in frequency tables. Data from the exploratory CCI Platform will not be included in the CSR but may be presented in a separate report.

9.3.4 Adverse Events

Where changes in severity are recorded in the Case Report Form, each separate severity of the adverse event (AE) will be reported in the listings, only the most severe will be used in the summary tables. A pre-existing condition is defined as an AE that starts before the participant has provided written informed consent and is ongoing at consent. A non-treatment emergent AE is defined as an AE which starts after informed consent but prior to dosing. A treatment-emergent AE is defined as an AE which occurs postdose or which is present prior to dosing and becomes more severe postdose.

All AEs will be listed. Treatment-emergent AEs will be summarized by study part and by infusion site location/study treatment, severity, and relationship to the study drug/protocol procedure. The frequency (the number of AEs, the number of participants experiencing an AE and the percentage of participants experiencing an AE) of treatment-emergent AEs will be summarized by infusion site location/study treatment, Medical Dictionary for Regulatory Activities (MedDRA) version 24.0 system organ class, and preferred term. The summary and frequency AE tables will be presented for all causalities and those considered related to the study drug by the investigator and repeated for those considered related to the protocol procedure. Any serious AEs will be listed. Summaries by infusion site location/study treatment will only be possible where a particular AE is able to be attributed to a particular infusion site location, AE data will also be summarized by study part.

Discontinuations due to AEs will be listed.

9.3.5 Concomitant Medication

Concomitant medication will be coded using the WHO drug dictionary (Version March 2021). Concomitant medication will be listed.

9.3.6 Clinical Laboratory Parameters

Samples for clinical laboratory data will be performed for inclusion/exclusion criteria purposes only and will not be presented.

9.3.7 Vital Signs

Vital signs data including subcutaneous layer thickness data will be listed.

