1.2. Schema

1.3. Schedule of Activities (SoA)

Table 1 Trial Flow Chart

Trial Period	Screening Period		Study Period	Follow-up-Televisit/early discontinuation	Comments
Visit no.	0	1	2 (Part A) CCI	4	
Timing	≥1 day before Visit 1	≤28 days prior to Visit 2	at least 3 days between Visit 2 and Visit 3	CCI	
In-house Visit/Period			see Table 2	CCI	
Informed consent	X	X			At Visit 1, check that informed consent has been signed and dated
Fasting		X			
Inclusion/exclusion criteria		X			At Visit 2, confirm participant compliance
Demographic data		X			
Smoking and alcohol consumption habits		X			
Medical history/Pre-existing Conditions		X			
Weight		X	X		
Height		X			
Alcohol breath test/urine drug screen		X	X		
Physical examination		X			
Vital signs		X	X		
12-lead ECG		X			
Haematology		X			
Biochemistry		X			
Coagulation		X			
Urinalysis		X			
Infectious serology		X			

Trial Period	Screening Period		Study Period	Follow-up- Televisit/early discontinuation	Comments
Visit no.	0	1	2 (Part A) CCI	4	
Timing	≥1 day before Visit 1	≤28 days prior to Visit 2	at least 3 days between Visit 2 and Visit 3	CCI	
In-house Visit/Period			see Table 2	CCI	
Pregnancy test		X	X		Only required for women of childbearing potential Serum at the screening visit and urine at Visits 2 and 3
FSH		X			This is only for women with both more than 12 months of amenorrhea and age of ≤55 (see Sections 10.2 and 10.4)
HbA1c		X			
Ultrasound			X		Thickness of the subcutaneous (SC) fat layer will be assessed at the abdominal areas (lower right and left), arm, thigh, and buttock.
Local Infusion site pain (VAS)			X		See Table 2 and Table 3 for collection times
Local Infusion site reactions			X		After removal of each infusion set
CCI Platform			X		Collect image of each local infusion site prior to insertion and after removal of each infusion set
AEs/Product Complaints		X	X	X	
Concomitant Medications		X	X	X	

Trial Period	Screening Period		Study Period		Follow-up- Televisit/early discontinuation	Comments
Visit no.	0	1	2 (Part A) CCI		4	
Timing	≥ 1 day before Visit 1	≤ 28 days prior to Visit 2	at least 3 days between Visit 2 and Visit 3		CCI	
In-house Visit/Period			see Table 2	CCI		
Meals (breakfast, lunch, and dinner)			X			Breakfast will be provided prior to study activities. Lunch will be provided after completion of the first bolus assessments. Dinner will be provided after completion of the second bolus assessments

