9.3. Statistical Analyses

Statistical analysis of this study will be the responsibility of Lilly or its designee.

Any change to the data analysis methods described in the protocol will require an amendment only if it changes a principal feature of the protocol. Any other change to the data analysis methods described in the protocol, and the justification for making the change, will be described in the statistical analysis plan (SAP) and the clinical study report. Additional exploratory analyses of the data will be conducted as deemed appropriate.

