9.3.1. General Considerations

Unless otherwise specified, these general considerations will apply to all analyses. Continuous variables will be summarized by the number of observations, mean, standard deviation, minimum, median, and maximum values. Categorical variables will be summarized by counts and percentages. Summaries will be provided by infusion site locations, including cannula depths, and study treatments (excipients).

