11. CHANGES FROM THE PROTOCOL SPECIFIED STATISTICAL ANALYSES

There were no changes from the protocol specified statistical analyses.

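### Does listing subcutaneous thickness without a by-site summary depart, undeclared, from the protocol's general summary rule?

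*SAP*

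**What the plan says.** The protocol collects the measurement site by site. The comment in the Schedule of Activities (Protocol 1.3) reads: "Thickness of the subcutaneous (SC) fat layer will be assessed at the abdominal areas (lower right and left), arm, thigh, and buttock". SAP 5.1, step 2, adds that the value is recorded in millimetres.

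Protocol 9.3.1 gives general considerations that hold by default, except where something else is specified. One is: "Continuous variables will be summarized by the number of observations, mean, standard deviation, minimum, median, and maximum values". The same paragraph says that summaries are broken down by infusion site location, with cannula depth, and by study treatment.

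The SAP handles thickness in section 9.3.7: "Vital signs data including subcutaneous layer thickness data will be listed". SAP 9.1 sets its own rule: "Summary statistics and statistical analysis will only be presented for data where detailed in this SAP". No SAP section details a summary of thickness, so none is planned.

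Three statements govern differences between the documents. Protocol 9.3 requires that a change of analysis method short of a principal feature be recorded: "the justification for making the change, will be described in the statistical analysis plan (SAP) and the clinical study report". SAP 3 says that the SAP supersedes the protocol's statistical considerations and that "where considerations are substantially different, they will be so identified". SAP 11 states: "There were no changes from the protocol specified statistical analyses".

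**The concern.** Thickness is continuous and is measured at exactly the locations being compared. Read word for word, Protocol 9.3.1 seems to call for n, mean, SD, minimum, median and maximum of thickness at each site and depth. The SAP provides none of these, and its section on changes reports nothing. That has the form of an undeclared departure.

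The subject matter adds weight. The study asks whether pain depends on infusion site and depth, and Protocol Table 6 gives the route as subcutaneous for both the 6 mm and the 9 mm cannula. In the unredacted text, thickness is the only collected variable that relates cannula length to the tissue at the site. If a promised summary had been dropped, readers would have to tally individual readings to describe the anatomy behind the site and depth ratios, and the statement in SAP 11 would be wrong.

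**Working it through.** **Does thickness enter any planned figure?** The one quantitative claim nearby is the power statement in Protocol 9.5 and SAP 7: 40 completers, a 55% increase, a log-scale SD of the within-participant difference of 0.95, and two-sided alpha 0.05.

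- Effect: ln(1.55) = 0.438.
- Standard error: 0.95/√40 = 0.150.
- Power of a paired t-test (noncentral t, 39 df): 0.812, which agrees with the stated figure of about 80%.

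Thickness is not an input. It is also absent from the mixed model in Protocol 9.3.2 and SAP 9.3.1, whose fixed effects are location, period, bolus time, VAS time point and the interactions of location with the two times, with participant as a random effect. Listing or tabulating thickness changes none of this.

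**How much data is affected?** 46 participants × 5 locations = 230 readings at most, or 40 × 5 = 200 for completers. All are listed.

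**What kind of rule is Protocol 9.3.1?** The rest comes from comparing the texts.

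1. The paragraph is a default attached to analyses. It fixes which statistics and strata to use and names no variable.
2. As a mandate for every continuous variable, it would reach much further than thickness:
   - Age, body weight, height and body mass index are summarised by study part (SAP 9.2).
   - Vital signs are listed only (SAP 9.3.7).
   - Screening laboratory and ECG data are not presented at all (SAP 9.3.6 and 9.3.8).

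   These are participant-level values. A participant has one body weight, not one for the 6 mm cannula and another for the 9 mm cannula, so a breakdown by depth has no meaning. The paragraph makes sense as a rule about the form of summaries that are produced.
3. Thickness is absent from the objectives and endpoints (Protocol 3), the hypotheses (9.1) and the unredacted text on primary, secondary, exploratory and safety analyses (9.3.2 to 9.3.5). Section 9.3.5 does foresee descriptive summaries of safety data, but only if event frequency allows, and it does not mention thickness. There is therefore no thickness analysis in the protocol for the SAP to remove.

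**Is SAP 11 then false?** It speaks of analyses that the protocol specifies, and none is specified for thickness. The duty in Protocol 9.3 attaches to methods described in the protocol, and no method for thickness is described. The duty in SAP 3 attaches to substantial differences. A descriptive table that bears on no objective, estimate or test would not reach that threshold even if the protocol had implied it.

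**Is the choice hidden?** No. SAP 9.3.7 says what happens to thickness, and SAP 9.1 says that anything not detailed is not summarised.

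**The case for a change.** The strongest reply is that the general rule, read literally, does cover thickness. Unlike body weight or vital signs, thickness can be broken down by location, so the absurdity that arises for participant-level data does not arise here. Precedence of the SAP settles which text governs, but it does not remove the separate duty in Protocol 9.3 to describe a change and its reason. One table from data already collected would show how thickness differs between sites. With 40 participants it would give each location's mean to within t(0.975, 39)/√40 = 0.32 SD. One sentence in SAP 11 would end the ambiguity.

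Part of this stands. The literal reading is arguable, and a by-site table would help a reader. It does not make a defect. A rule that cannot sensibly be applied to the other continuous variables is better read as a rule of form, and on that reading there is nothing to declare. The table also remains available: Protocol 9.3 foresees additional exploratory analyses, and SAP 3 allows supplementary ones identified in the study report.

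Two possible extensions are weaker still. A count of readings below cannula length would be hard to interpret, because the visible text does not say whether the reading includes skin or at what angle the cannula enters. A plot of the 9 mm versus 6 mm pain difference against thickness would be imprecise. Assume normally distributed thickness, a 55% effect confined to the thinnest 10–30% of participants, and a correlation of 0.3–0.8 between boluses. Simulated power for the slope is then only 8–26%. None of those inputs comes from the documents.

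**Conclusion.** The concern does not hold. The plan lists thickness, says so, and leaves no stated objective unanswered. The statement in SAP 11 is not shown to be wrong, because the protocol specifies no thickness analysis from which the SAP could depart. Up to 230 readings are presented individually and not in a table. The effect on the primary and secondary comparisons, their intervals and the sample size is nil.

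The conclusion rests on reading Protocol 9.3.1 as a rule for the form of summaries, which its default wording and the handling of demographics, vital signs and screening data support. It also rests on the unredacted text, since parts of Protocol 9.3 are blacked out. Wanting a by-site thickness table is a fair preference about presentation, and it changes no result.
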